## **Background & Rationale**

Pulse oximeters are commonly utilized medical devices used to measure blood oxygen saturation (SpO2)[2]. These devices (such as the INNOVO Fingertip Pulse Oximeter) are either stand-alone or integrated into physiologic monitoring systems, using 2 wavelengths of lights to determine SpO2. With recent advances in technology, Spatial Frequency Domain Imaging (SFDI) using range of light wavelengths from red to near infrared (NIR) such as in Clarifi(R) (Modulated Imaging, Inc., Irvine CA), smartphones such as Apple Watch (Apple Inc., Cupertino, CA), transcutaneous oximetry TCOM (Perimed Inc., Las Vegas, NV) now have pulse oximetry capabilities. Since it is possible that most patients could utilize this technology, we sought to assess the accuracy, reliability and usability of these oximeters and compare outcomes. In this study, a cohort of 20 healthy volunteers above the age of 18 including males and females of different skin colors will be assessed at the same site and data will be compared. We aim to provide a set of data that will support the clinical and scientific community and identify more than one reliable skin oxygen measurement modalities. The Innovo pulse oximeter device will be used for all subjects.

#### 1.0 **Objective(s)**

**1.1 Primary Objective** 

To investigate multiplatform for tissue oxygen measurement devices

**1.2** Secondary Objective

To compare other modalities with FDA approved Pulse Oximetry

## **1.3 Tertiary/Exploratory/Correlative Objectives**

To investigate skin color biasness in the optical Oximeters. Fitzpatrick's skin type chart will be used to evaluate skin type.

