## 4.0 Study Design

## 5.0 Enrollment/Randomization

Potential subjects will be identified from IU School of Medicine staff members. Each subject will use all four devices.

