## 6.0 Study Procedures

First the subjects will go through a questionnaire session about their medical history by a designated study team member. The questionnaire data will be placed in RedCap using a subject ID that cannot be linked back to the subject. Then the subject will be consented. Subject will be enrolled. Then the non-invasive data collecting procedure will start on the following equipment:

Spatial Frequency Domain Imaging (SFDI): During consenting period, the Modulim equipment will be calibrated and setup ready for scanning. Subject's volar aspect of the thumb along with the palm surface

will be ready to target the optical camera head. Actual scanning takes less than 60 seconds. The images will be processed offline. During processing 3-5 different regions of interest (ROI) will be taken to measure the oxygen parameters such as tissue oxygen saturation (StO2), oxy-hemoglobin (HbO2), deoxy-hemoglobin (HbR), superficial hemoglobin (HbT1, sub-surface hemoglobin (HbT2). The model used is a Clarifi Modulum

**Transcutaneous oxygen monitoring (TCOM)**: Transcutaneous oxygen monitoring (TCOM or TcpO2) is a noninvasive, clinically-approved method to obtain skin oxygen levels. The method is quantitative, and measures oxygen delivery to the skin from underlying tissue. Before positioning the electrode, an adhesive fixation ring will be placed on the dry skin on the volar aspect of the thumb and an electrolyte as a contact liquid will be filled half and the probe is aligned into it by rotating clock-wise to fasten it. Recording will be started and waited for the oxygen level to stabilize and a fixed value will be recorded. The model used is a Perimed PeriFlux 5000. The probe will be heated to about 45°C. Although this device has other options, only the measurement of  $O_2$  will be performed using this device.

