Statistical Analysis Plan

Protocol Title

Measurement of Oxygen Saturation in healthy human volunteers before, during and after hyperemic events using Multi-Modal Techniques: Spatial Frequency Domain Imaging (SFDI), transcutaneous oxygen measurement (TCOM), Pulse Oximeter, and Apple Watch.

Principal Investigator:

[name]. Assistant Professor, Indiana Center for Regenerative Medicine and Engineering at Indiana University Department of Surgery, Division of Plastic Surgery School of Medicine, Indiana University Analysis will be performed based on search of answers for the questions designed.

Q1: What are the correlations between the measurements we've taken? Are those correlations significant?

The repeated measures correlations for the measurements. Use repeated measures correlation because we have repeated measures for our data (we get values for each measurement four separate times).

Q2: What are the differences between males' and females' measurements, over time?

We have 20 subjects (13 male, 7 female). We have 5 parameters for each subject: StO2, HbO2, HbR, HbT1, and HBT2. Each measurement will be recorded at 4 time points: baseline, occlusion, reactive hyperemia, and recovery. Plots showing how subjects' measurements changed over time will be obtained. The mean measurement value for males and females, over time will be obtained. Hypothesized that males' and females' measurements follow similar patterns over time. StO2 for males will have higher average HbO2, HbR, HbT1 and HbT2 measurements than females, over all time points compared to females.

Q3. Is this male/female gap in measurements statistically significant, though?

To answer this, I fit multivariate linear regression models at each time point. Results of multivariate linear regression models, for each time point will be obtained. Multivariate models are basically just regression models with multiple outcome variables; in this case, the outcomes are the 5 measurements. The regression coefficients for the intercepts are basically the estimated average measurement for males, for that measurement, at that time point; the p values for the intercepts don't really matter. The regression coefficients for female is just the estimated average difference between males and females, for that measurement, at that time point.

Example:

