For StO2 at time 1, it's estimated that type 2s and 3s have an StO2 value of 71, with a 95% confidence interval of 63 to 78. It's estimated that type 4s have StO2 values at time 1 that are 20 lower than type 2s and 3s, on average [95% confidence interval ranges from 33 lower than 2s and 3s, to 7 lower than 2s and 3s]. That confidence interval [-33 to -7] does not contain 0, meaning we're confident that the difference between 4s and 2s/3s is not 0. Because of that, the p value for Time 1/StO2/Female is 0.004, which is less than .05, which means we can reject the idea that 4s and 2s/3s have the same StO2 values at time 1. Most of the 5 measurements are correlated with one another. Females and males had similar measurements at baseline, but started to differ in HbO2, HbR, HbT1, and HbT2 from inflation onwards. Those with skin type 4 had lower StO2, higher HbR, and higher HbT1 compared to those with skin type 2 and 3, at all-time points; the two groups didn't significantly differ in regard to HbO2 and HbT2 at any time.

Abbreviation StO2= tissue oxygen saturation HbO2=oxy hemoglobin HbR= deoxy hemoglobin HbT1= superficial perfusion hemoglobin HbT2= deep perfusion hemoglobin TCOM=trans-cutaneous oxygen measurement

SFDI=spatial frequency domain imaging

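### The skin-colour objective is bias in the optical oximeters, but the SAP compares only SFDI readings between skin types, so it cannot show device bias, and the other three devices are not analysed by skin type

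*Protocol*

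**What the plan says.** Protocol section 1.3 sets the exploratory aim as "To investigate skin color biasness in the optical Oximeters" and adds that "Fitzpatrick's skin type chart will be used to evaluate skin type". Section 2.3 lists a different kind of outcome for the same tier: oxygenation of melanin-rich or scarred tissue against normal skin, which is a physiological comparison and not a device error.

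Protocol section 5.0 states "Each subject will use all four devices". In section 6.0 the SFDI system, the Apple Watch and the pulse oximeter are described as working with light. TCOM is described differently: "Before positioning the electrode, an adhesive fixation ring will be placed on the dry skin on the volar aspect of the thumb", with an electrolyte as contact liquid and a probe heated to about 45°C. Of TCOM the protocol says "The method is quantitative, and measures oxygen delivery to the skin from underlying tissue".

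The SAP states "We have 5 parameters for each subject: StO2, HbO2, HbR, HbT1, and HBT2". Protocol section 6.0 shows that these are the SFDI image outputs: "During processing 3-5 different regions of interest (ROI) will be taken to measure the oxygen parameters such as tissue oxygen saturation", followed by the same list. The SAP's skin-type question (the second item numbered Q2) fits a separate multivariate regression at each time point, with skin type as the only predictor described. It concludes "Those with skin type 4 had lower StO2, higher HbR, and higher HbT1 compared to those with skin type 2 and 3". TCOM appears in the SAP only in the title and the abbreviation list. The SAP's first question, on correlations, does not involve skin type.

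**The concern.** Bias is the reading minus the truth, and skin-colour bias is an error of that kind that changes with skin type. To estimate it, an analysis needs either a reference value or a comparison with a device that does not share the error. The SAP has neither. It estimates a difference between groups of people on one optical device.

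Two readers can therefore take opposite messages from the same result: that SFDI under-reads in darker skin, or that type IV subjects have lower tissue oxygen. The first is a fault in the device and the second is a finding about people. The protocol holds both readings, in sections 1.3 and 2.3, and the SAP's conclusion does not say which is meant. Section 1.3 also speaks of oximeters in the plural, yet the pulse oximeter and the watch enter no skin-type analysis.

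**Working it through.** **Step 1. Reproduce the SAP's figure.** Inputs from the SAP's skin-type example: difference -20, 95% CI -33 to -7, p = 0.004. With 20 subjects and two coefficients there are 18 degrees of freedom.

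- CI half-width = (33 - 7)/2 = 13
- SE = 13/2.101 = 6.19
- t = -20/6.19 = -3.23
- two-sided p = 0.0046 (0.0035 to 0.0060 when the estimate and limits vary within rounding)

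This agrees with the stated 0.004. The arithmetic is not the problem. (The SAP labels this p value as belonging to the female coefficient, which looks like a carry-over from the sex example.)

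**Step 2. What the coefficient contains.** Let T be the true difference in tissue oxygenation and B the optical error that depends on skin type. The model estimates only T + B = -20. The pairs (T = -20, B = 0) and (T = 0, B = -20) give the same coefficient, interval and p value. More subjects would narrow the interval for T + B without separating T from B.

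**Step 3. Group sizes and SD (inferred, not stated).** The II and III mean is 71 (63 to 78), a half-width of 7.5. The variance of that mean is s²/n₀, and that of the difference is s²(1/n₀ + 1/n₁), so

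n₀/n₁ = (13/7.5)² - 1 = 2.0 (1.4 to 2.7 with rounding).

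Of 20 subjects this suggests about 13 in II and III and 7 in IV. (The match with the sex split of 13 and 7 is not where the figure comes from.) Then s = 6.19/√(1/13 + 1/7) = 6.19/0.469 = 13.2 points, and the gap is 20/13.2 = 1.52 SD.

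**Step 4. What a contrast with TCOM could add.** Scale each device by its within-group SD and take SFDI minus TCOM within subject. If a true difference affects both devices equally in SD units (an assumption), the skin-type coefficient of this difference estimates B. For SFDI-TCOM correlation r, which the documents do not give, the 95% CI half-width is

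2.101 × √(1/13 + 1/7) × √(2(1 - r)) = 0.985 × √(2(1 - r)).

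The last three columns come from a simulation of 20,000 runs per scenario with a total SFDI gap of 1.52 SD. They give the share of runs in which the contrast is significant at 0.05.

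| r | Half-width, SD | In StO2 points | Gap all real | Gap all optical | Half and half |
|---|---|---|---|---|---|
| 0.3 | 1.17 | 15 | 5% | 74% | 25% |
| 0.5 | 0.98 | 13 | 5% | 86% | 33% |
| 0.7 | 0.76 | 10 | 5% | 98% | 50% |

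In the same runs the SAP's own SFDI test is significant in about 86% whether the gap is all real or all optical. A skin-type test on TCOM alone reaches 80% power only for differences of about 1.4 SD or more.

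**The case against.** The strongest reply is that the objective is exploratory, that section 2.3 lists a descriptive outcome which the SAP's skin-type part roughly delivers, and that the SAP never claims to have shown bias. This stands as a limit on severity. It does not close the gap between section 1.3 and the analysis.

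A second reply is that TCOM is a weak reference. It measures a different quantity, on another scale, at a heated site. A real StO2 difference need not appear in TCOM at the same size, so a contrast away from zero does not single out bias. That TCOM uses no light is inferred from the electrode description in section 6.0, while the Background loosely groups TCOM with devices that have pulse oximetry capability. All of this stands, and TCOM can be used only as a partial comparator.

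Three stronger readings are tempting, and the documents support none of them:

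- *TCOM would settle the matter, and gaps in the same direction on SFDI and TCOM would clear SFDI.* With no true difference, the TCOM estimate still falls on the same side as the SFDI gap about half the time, so agreement in sign carries little information.
- *The pattern itself, higher HbR with HbO2 unchanged, points to melanin.* The SAP first describes HbO2 as lower on average in type IV and later says only that the groups did not differ significantly, which is not the same as unchanged. The documents give no absorption data for melanin.
- *The other optical devices can be ignored because they share any artefact.* The documents do not say so. Section 6.0 describes pulse oximetry as isolating the arterial compartment, which differs from a tissue reading.

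**Conclusion.** The concern holds in this form: the skin-type analysis cannot show device bias and leaves out three of the four devices. The whole 20-point gap (7 to 33) is unattributed. A reader might infer that SFDI is biased in darker skin, or that type IV subjects are less well oxygenated. The SAP's analysis supports neither; it supports only a difference in SFDI readings.

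That part rests on the documents alone. The figures on what a TCOM contrast could achieve rest on assumptions: 13 against 7 subjects, r from 0.3 to 0.7, and an equal standardised true effect on both devices. On those, the contrast could often tell the two extreme explanations apart but would usually not resolve a mixed one. Severity is low to moderate.

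**What to change.** In the SAP's skin-type section:

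1. Report the baseline difference between types II and III and type IV, with 95% CI and group sizes, for each of the four devices. Baseline is suitable because section 6.0 has the TCOM value recorded once it has stabilised.
2. Add the standardised skin type by device contrast, SFDI minus TCOM. Divide each subject's reading by that device's within-group SD, take the difference within subject, and regress it on skin type.
3. State how it will be read: by the estimate and interval of the contrast, not by whether the two gaps share a sign. An interval excluding zero is compatible with optical bias but does not prove it. An interval including zero is inconclusive.
4. Label the analysis as added after the SFDI results were seen, since the SAP already reports fitted models.
5. Word the existing conclusion as a *difference in SFDI readings between skin types*, not as a difference in oxygenation and not as bias.

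If the contrast is not added, restate the objective in section 1.3 as a descriptive comparison of SFDI readings by skin type, and bring section 2.3 into line.

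The cost is SAP wording and a few models on data the protocol already has recorded. The downside is an imprecise contrast against a partial reference. Because the scaling SDs are themselves estimated, the half-widths shown are slightly optimistic. The rewording in item 5 is worth making even if the contrast proves inconclusive.

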## 2.0 Outcome Measures/Endpoints

## 2.1 Primary Outcome Measures

Oxygen in tissue and blood measured non-invasively

## 2.2 Secondary Outcome Measures

Comparison of the devices provides the standard for clinical use

2.3 Tertiary/Exploratory/Correlative Outcome Measures Melanin or scarred tissue oxygenation compared to normal skin

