## 3.0 Eligibility Criteria

## 3.1 Inclusion Criteria

- Healthy volunteers
- Able to understand and complete the Informed Consent
- Both males and females
- Age between 18-65 years
- All ethnic backgrounds

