## 3.2 Exclusion Criteria

- Patients or limited health conditions
- Under the age of 18 years or above the age of 65 years
- Smoking tobacco product
- Prisoners
- Cannot consent for themselves

• Pregnant individuals

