**Apple Watch Oxygen Sensor**: Smart watch blood oxygen sensors also measure blood oxygen level in the tissue. Apple Watch Series 6 introduced this new feature for monitoring blood oxygen level using light emitting diodes (LEDs) at the back of apple watches. A low blood oxygen level can be indicative of a serious health issue that needs immediate attention. The apple watch is equipped with green, red, and infrared LEDs that shine light onto the blood vessels in the wrist, with photodiodes measuring the amount of light reflected back. Apple's algorithms use this information to calculate the color of the blood, which is an indication of how much oxygen is in the blood. Bright red blood is well oxygenated, while darker blood has less oxygen. This can measure blood oxygen levels between 70 and 100 percent. Most healthy people have blood oxygen levels that range from 95 to 100 percent. The apple watch sensor will be positioned on the user's preferred wrist.

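### Healthy volunteers near 95–100% saturation, with no arterial reference, can show watch–oximeter agreement at normal saturation but not accuracy at low saturation or a clinical standard

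*Protocol*

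**What the plan says.** The protocol makes two claims about what the comparison will deliver. The Background & Rationale states that "we sought to assess the accuracy, reliability and usability of these oximeters and compare outcomes", and gives as its reason that most patients could come to use the technology. Section 2.2 gives the secondary outcome as "Comparison of the devices provides the standard for clinical use". The matching objective, in section 1.2, is "To compare other modalities with FDA approved Pulse Oximetry".

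The population is set in sections 3.1 and 3.2. Inclusion requires "Healthy volunteers"; the exclusions include "Patients or limited health conditions" and "Smoking tobacco product".

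Section 6.0, in the Apple Watch paragraph, says of the watch: "This can measure blood oxygen levels between 70 and 100 percent". It then says: "Most healthy people have blood oxygen levels that range from 95 to 100 percent". The same paragraph presents a low level as the clinically important finding. The only provocation in section 6.0 is a pressure cuff at 200 mmHg for 2 minutes, with data at baseline, during occlusion and after release.

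For analysis, section 9.0 of the protocol plans a mean and a standard error. The SAP names five parameters, all of them SFDI outputs, and contains no comparison of any device with the oximeter.

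**The concern.** The stated outcome and aim ask for more than the sample can give. A standard for clinical use, or a statement about accuracy in patients, needs information at the saturations where a clinical decision arises. This sample is expected to lie almost wholly at the top of the scale, and the comparator is another oximeter, not an arterial measurement.

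The risk is a wrong conclusion in either direction. In a narrow range, a small mean difference can look like good performance for a device that fails at low saturation, and a weak correlation can look like failure for two sound devices. Either result could be carried over to patients, whom the trial excluded.

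**Working it through.** The plan contains no accuracy, agreement or sample-size calculation, so there is no figure of its own to reproduce. The check has two parts.

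**1. What range do the SpO2 devices see?**

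- Expected range in healthy people: 95–100%, width 5 (protocol 6.0, stated for most healthy people).
- Watch range: 70–100%, width 30 (protocol 6.0).
- Share covered: 5/30 = 17%.
- Steps that lower systemic arterial saturation: none described. The cuff stops flow to one arm. The pulse oximeter paragraph of 6.0 says that SpO2 is derived from the arterial compartment alone.
- Arterial reference: none named. A reading taken during occlusion therefore could not be judged right or wrong, whatever the device displays.

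**2. What does a narrow range do to the usual summaries?** This part is illustration. The documents give neither the spread nor the error SDs. I assume true SpO2 uniform over the range and, for each single reading, independent error with SD e = 1, 2 or 3 points.

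Variance of true values: V = width²/12.
- Width 5: V = 25/12 = 2.08, SD 1.44.
- Width 30: V = 900/12 = 75, SD 8.66.

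Expected correlation of two unbiased devices: V/(V + e²).

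| e | 95–100% | 70–100% |
|---|---|---|
| 1 | 2.08/3.08 = 0.68 | 75/76 = 0.99 |
| 2 | 2.08/6.08 = 0.34 | 75/79 = 0.95 |
| 3 | 2.08/11.08 = 0.19 | 75/84 = 0.89 |

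If five readings per device were averaged, e² becomes e²/5, and the 95–100% values rise to 0.91, 0.72 and 0.54.

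Standard error of a calibration slope with n = 20 and an error-free reference: e/(SD × √19). At e = 2 this is 2/(1.44 × 4.36) = 0.32 over 95–100%, and 2/(8.66 × 4.36) = 0.05 over 70–100%.

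Two examples show what the narrow range hides:
- A device with slope 0.8 that is correct at 97.5% is off by 0.2 × 2.5 = 0.5 point at 95%, but by 0.2 × 17.5 = 3.5 points at 80%. The slope's departure from 1 is 0.2, less than one standard error (0.32) in the narrow range.
- A device that always displayed 97.5% would have a root-mean-square error of only 1.44 points over 95–100%. A constant mid-range display over 70–100% would have 8.66.

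**The case against.** The strongest reply is that the range argument reaches only two of the four devices, and this stands. A reader might infer that the whole device comparison is empty, but the documents do not support that. The SAP's worked examples give baseline StO2 of 62 in males and 71 in skin types II and III, with type IV 20 lower (71 − 20 = 51). SFDI is plainly not confined to 95–100%, and neither it nor TCOM is tied to arterial saturation. Both can be described across baseline, occlusion and hyperemia. Their limit is a different one: they measure other quantities than SpO2. It follows that the secondary outcome should not be cut down to the watch and oximeter at rest, which would conflict with section 1.2 and with the study title.

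Four further points on the other side have weight:

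- The correlations are expected values under assumptions, not upper limits. Averaging or shared error would raise them, and additive error ignores the ceiling at 100%.
- A reader might infer that a watch–oximeter correlation is planned. None is specified. The SAP's repeated measures correlation appears to concern the five SFDI parameters.
- The documents do not say what either SpO2 device displays during occlusion. That an oximeter loses a dependable signal without flow is physiological reasoning. The point does not need it, because no arterial reference is taken at any phase.
- The 95–100% figure is for most healthy people, so a few readings may fall lower. Accuracy appears as an aim only in the Background.

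None of this restores the section 2.2 claim. No combination of these data sets a standard for clinical use.

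**Conclusion.** The point holds for the two SpO2 devices and for the clinical-standard claim. By the protocol's own figures, the watch and oximeter will be compared mainly over about 5 of 30 points (17%), with no arterial reference. That supports a description of agreement near normal saturation in healthy adults. It does not support a statement about accuracy at low saturation, nor a standard for clinical use.

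This conclusion rests on the eligibility rules, the stated 95–100% range, the absence of any described step that lowers systemic saturation, and the absence of an arterial reference. It does not depend on the illustrative correlations, which assume a uniform spread and independent errors of 1 to 3 points.

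The stronger reading, that the trial can support no device comparison at all, is not justified: descriptive comparison across phases remains possible for every modality. The data stay usable; what must change is what may be concluded from them.

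**What to change.** - **Protocol 2.2:** replace the clinical-standard wording with: *descriptive comparison of SFDI, TCOM and Apple Watch with the Innovo pulse oximeter in healthy adults at each phase, with watch–oximeter agreement (mean paired difference and limits of agreement) at rest over the observed SpO2 range*.
- **Background & Rationale:** replace accuracy with *agreement with the pulse oximeter in healthy adults*.
- **SAP:** add the watch–oximeter agreement analysis, since no device-against-oximeter analysis exists now. State whether the five sets of data in protocol section 9.0 are repeat readings on a subject and, if so, how the limits of agreement allow for them.
- **Reporting:** give the observed SpO2 range beside each watch–oximeter result. Do not use a correlation over that range as evidence for or against agreement. State that no conclusion is drawn below the lowest observed SpO2 or about clinical use.

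The cost is a less ambitious claim and a small added analysis. No new participants, procedures or data are needed.

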Pulse Oximeter for Oxygen Monitoring: The pulse oximeter enables transcutaneous monitoring of the oxygen saturation of hemoglobin in arterial blood ( $StO_2$ ). Pulse oximetry is so widely prevalent in medical care that it is often regarded as a fifth vital sign[3]. It is important to understand how the technology functions as well as its limitations. To recognize the settings in which pulse oximeter readings of oxygen saturation (SpO2), an understanding of two basic principles of pulse oximetry is required: (i) how oxyhemoglobin (HbO2) is distinguished from deoxyhemoglobin (HbR) and (ii) how the SpO2 is calculated only from the arterial compartment of blood. Pulse oximetry is based on the principle that HbO2 and HbR differentially absorb red and near-infrared (IR) light. It is fortuitous that HbO2 and HbR have significant differences in absorption at red and near-IR light because these two wavelengths penetrate tissues well whereas blue, green, yellow, and far-IR light are significantly absorbed by non-vascular tissues and water [3]. HbO2 absorbs greater amounts of IR light and lower amounts of red light than does HbR; this is consistent with experience – well-oxygenated blood with its higher concentrations of  $HbO_2$  appears bright red to the eye because it scatters more red light than does HbR. On the other hand, HHR absorb more red light and appears less red. Exploiting this difference in light absorption properties between HbO2 and HbR, pulse oximeters emit two wavelengths of light, red at 660 nm and near-IR at 940 nm from a pair of small light-emitting diodes located in one arm of the finger probe. The light that is transmitted through the finger is then detected by a photodiode on the opposite arm of the probe. In this study, volar aspect of thumb and index finder of the subject will be used to measure SpO2. The model is Innovo iP 900AP.

Sequence of the events during the study visit:

- 1) Consenting and enrolling the subjects
- 2) Medical questionnaire
- 3) Fitzpatrick's skin type assessment

- 4) Non-invasive imaging and data collection of the thumb and index fingers with the above devices in the following order:
  - a) Baseline imaging and data collection

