For StO2 at time 1, it's estimated that males have an StO2 value of 62, with a 95% confidence interval of 54 to 70. It's estimated that females have StO2 values at time 1 that are 4 higher than males, on average [95% confidence interval ranges from 11 lower than males, to 19 higher than males]. That confidence interval [-11 to 19] contains 0, so there's a strong enough possibility that the difference between male and female StO2 values at time 1 is 0 (i.e. there's no difference). Because of that, the p value for Time 1/StO2/Female is 0.581, which is greater than .05, which

means we can't reject the idea the females and males have the same StO2 values at time 1.

Q2: Instead of gender, what about differences between skin type (II and III vs. IV)?

Plot of measurements over time for subjects with skin type II and III vs. skin type IV will be analyzed. The data represent the mean measurement value for skin types 2 and 3 vs skin type 4, over time. Based on the above plots, it appears that (on average) those with skin type 4 have lower StO2 and HbO2 over time, compared to those with skin type 2 and 3. Skin type 4s appear to have higher HbR and HbT1 over time, compared to skin type II and III. There's a lot of variation in HBT2 over time, and both skin type groups have similar mean values over time. Like for gender, I fit separate multivariate linear regression models for each time point. The regression coefficients for the intercepts are basically the estimated average measurement for the skin type II + III group, for that measurement, at that time point; the p values for the intercepts don't really matter. The regression coefficients for skin type IV is just the estimated average difference between 4s and 2s + 3s, for that measurement, at that time point.

Example:

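### Section 2.2 compares SFDI and TCOM with the pulse oximeter although they measure different quantities, so a comparison of values would present that difference as inaccuracy

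*Protocol*

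**What the plan says.** The Background sets out to "assess the accuracy, reliability and usability of these oximeters and compare outcomes". The secondary objective (Protocol 1.2) is "To compare other modalities with FDA approved Pulse Oximetry", and the secondary outcome (Protocol 2.2) reads "Comparison of the devices provides the standard for clinical use". No metric, common scale or acceptable difference is given. Section 9.0 plans a mean and standard error for each device and nothing else.

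Section 6.0 describes what each device reports:

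- **SFDI:** tissue oxygen saturation, StO2, with four haemoglobin parameters.
- **TCOM:** TcpO2, a skin oxygen level. The text says "The method is quantitative, and measures oxygen delivery to the skin from underlying tissue" and does not call it a haemoglobin saturation.
- **Pulse oximeter:** "The pulse oximeter enables transcutaneous monitoring of the oxygen saturation of hemoglobin in arterial blood". This quantity is given the symbol StO2 at that point and SpO2 later in the same paragraph.
- **Apple Watch:** blood oxygen in percent, read at the wrist.

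The study title, as printed in the SAP, puts all four under one term: "Measurement of Oxygen Saturation in healthy human volunteers before, during and after hyperemic events using Multi-Modal Techniques". The SAP's group comparisons use the five SFDI parameters only. It has no oximeter, watch or TCOM variable and no cross-device analysis.

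**The concern.** Comparing values with a reference tests accuracy only when both devices aim at the same quantity. Here one reference, arterial saturation, is set against a tissue saturation and a skin oxygen level. A gap between SFDI and the oximeter would then mix three things: the difference in what is measured, any optical bias, and measurement error. The plan offers no way to separate them. For TCOM, the documents do not give even a unit in which a difference could be expressed.

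At stake is the secondary conclusion. If device means are tabulated beside the oximeter's and read under the accuracy aim, SFDI could be reported as reading far too low in healthy people when it may be working as intended. A statement about a clinical standard would then have no basis for two of the three comparators. Using StO2 for both the arterial and the tissue quantity makes that misreading easier.

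**Working it through.** The documents give no agreement limit, power or sample-size figure for the device comparison, so there is no design figure to reproduce. The check is whether the SAP's StO2 figures are usable and, if so, how far they lie from the protocol's blood-oxygen range.

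**Inputs**

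- SAP, Q3 example, time 1: "males have an StO2 value of 62, with a 95% confidence interval of 54 to 70". Females are 4 higher (95% CI -11 to 19).
- SAP, skin-type example, time 1: types II/III 71 (63 to 78). Type IV is 20 lower (-33 to -7).
- SAP: 20 subjects, 13 male and 7 female.
- Protocol 6.0, Apple Watch: "Most healthy people have blood oxygen levels that range from 95 to 100 percent".

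**Step 1. Are the SAP figures internally usable?** SE = CI width / (2 × t), with t(0.975, 18 df) = 2.101.

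- Sex: 30 / 4.202 = 7.14; 4 / 7.14 = 0.56; p = 0.582 (stated 0.581).
- Skin type: 26 / 4.202 = 6.19; -20 / 6.19 = -3.23; p = 0.0046 (stated 0.004; rounding of the inputs allows 0.003 to 0.007).

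Both p values are consistent with their intervals.

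**Step 2. Pooled StO2 at time 1.** The female mean is 62 + 4 = 66. Pooled: (13 × 62 + 7 × 66) / 20 = 1268 / 20 = 63.4.

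**Step 3. Distance from 95 to 100.**

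| StO2 figure | Value | Below 95 | Below 100 |
|---|---|---|---|
| Pooled | 63.4 | 31.6 | 36.6 |
| Males | 62 | 33 | 38 |
| Females | 66 | 29 | 34 |
| Types II/III | 71 | 24 | 29 |
| Type IV (71 - 20) | 51 | 44 | 49 |
| Upper CI limit, males | 70 | 25 | 30 |
| Upper CI limit, types II/III | 78 | 17 | 22 |

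The gap does not depend on the subgroup chosen or on sampling error in the mean: even the upper confidence limit for types II/III falls 17 points short of 95.

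**Step 4. How much could be skin-type bias?** The pooled mean is 71 - 63.4 = 7.6 points below the type II/III mean. If the whole type IV deficit were optical bias, it would account for about 7.6 points of the pooled gap, and types II/III alone would still be 24 to 29 below the range. The documents cannot say whether types II/III are themselves free of bias.

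**Step 5. Which analysis would show the gap?** A comparison of means would. A correlation would not, because adding a constant to one variable leaves it unchanged; in a simulated check it was 0.830 with and without a 34-point shift.

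**TCOM.** The documents give no value and no unit, so nothing can be computed.

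**The case against.** The strongest reply is that the protocol knows its quantities differ. Section 2.1 names tissue and blood oxygen, section 6.0 describes StO2, TcpO2 and arterial saturation separately, and the SAP defines StO2 as tissue saturation. The StO2 label on the oximeter looks like a single slip. This stands. A reader might infer that the plan treats all readings as one quantity throughout, and that goes too far. The single term is in the title, and the difficulty arises where the objective and section 2.2 set the devices against one reference without carrying the distinction over.

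A reader might also infer that devices will be ranked by closeness to the oximeter. No document says so. The objective says compare, section 2.2 gives no metric, and the SAP has no cross-device analysis. The harm therefore depends on values being compared. That is the natural reading of an accuracy aim, a named reference and per-device means, but it is not a written analysis. The SAP's silence does not protect against it, because the secondary objective still stands with no valid way to meet it.

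Third, a reader might quote the gap as 24 to 49 points and attribute all of it to the measurand. That range joins opposite subgroup extremes. Its upper end also contains the 20-point skin-type difference, while section 1.3 makes skin-colour bias in the optical devices a study question. That part may be device bias.

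Finally, matching SFDI and TCOM on the size of percent change would be no remedy. They are different quantities too, and their percent changes need not agree when both devices work correctly.

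**Conclusion.** The point holds in a limited form. The secondary comparison uses one reference for quantities that the protocol itself describes as different, and section 2.2 attaches a clinical-standard claim to it. Compared by value, SFDI would sit roughly 32 to 37 points below the oximeter scale at time 1.

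That size assumes that the SAP's example means are StO2 in percent (no unit is printed), that the 13 to 7 weights apply, and that 95 to 100 describes these volunteers. The last is a general remark in the Apple Watch section and not measured SpO2, but a shift of a few points would not change the conclusion. The figure is an apparent gap and not an estimate of a pure measurand effect, since some of it could be skin-type bias. For TCOM the documents support only that the quantity differs; no size can be given. They do not support saying that the plan will rank the devices by closeness, or that the whole gap is free of device fault.

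**What to change.** Revise section 2.2, with a matching SAP section, before any device comparison is reported:

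- **(a) Watch against oximeter.** Restrict value agreement to this pair: mean difference with limits of agreement, in SpO2 percentage points. State that the watch reads at the wrist and the oximeter at the finger, so the difference includes any site effect.
- **(b) SFDI and TCOM.** Make no value-agreement or accuracy claim against the oximeter. Report StO2 and TcpO2 each in its own stated unit, as within-subject change from baseline across the planned phases. Across devices, compare only direction or association, not the size of percent change. Section 6.0 records TCOM once the level has stabilised, while the occlusion lasts 2 minutes, so use TCOM occlusion values only where a stabilised reading was obtained, and report how many there are.
- **(c) Clinical-standard claim.** Delete the wording "Comparison of the devices provides the standard for clinical use".
- **(d) Symbol.** In the pulse oximeter paragraph of section 6.0, change the symbol for arterial saturation to SpO2.

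The cost is a change of wording and analysis plan, with no new measurements. The secondary claim narrows to one agreement comparison plus descriptive response comparisons, and the TCOM occlusion data may be incomplete.
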